Objectives	
Phase I Primary Objectives:
 
 • To determine the safety of fixed doses of DEC205mAb-NY-ESO-1 fusion protein with adjuvant poly-ICLC given as a vaccine in combination with INCB024360. • To evaluate toxicity as defined by NCI Common Terminology Criteria for Adverse Events (CTCAE) Version 4.0. 
Phase IIb Primary Objective:
 
 • To determine the progression free survival (PFS) (primary endpoint) using irRC criteria. 
Phase I and Phase IIb Secondary Objectives
 
 • To determine the effectiveness of INCB024360 on enhancing vaccine efficacy by assessing NY-ESO-1 specific cellular and humoral immunity. • Exploratory Cohort at Roswell Park ONLY: To determine the effectiveness of Sirolimus on enhancing vaccine efficacy by assessing NY-ESO-1 specific cellular and humoral immunity. 
 ○ Peripheral blood NY-ESO-1 specific CD8+ and CD4+ T cells. ○ Peripheral blood NY-ESO-1 specific antibodies. ○ Peripheral blood frequency of CD4+CD25+FOXP3+ regulatory T cells. ○ Pharmacokinetics of INCB024360 in relation to T cell frequency and function in correlation with PFS.
Study Design	
This is an open-label, Phase I/IIb study of the IDO inhibitor, INCB024360, in combination with DEC205mAb-NY-ESO-1 fusion protein (CDX-1401) given with adjuvant poly-ICLC in patients with NY-ESO-1 or LAGE-1 expressing epithelial ovarian, fallopian tube, or primary peritoneal cancer who are in remission.
 
For the Phase I component of the study, eligible patients will receive a fixed intracutaneous dose of DEC205mAb-NY-ESO-1 fusion protein (CDX-1401) (Day 1) given with subcutaneous adjuvant poly-ICLC (Day 1 and Day 2) for each 28 day cycle for a total of 5 cycles; and Cohort 1 patient enrollment will begin INCB024360 at a fixed daily dose of 300 mg BID orally (Cohort 1) for a total of 7 cycles. Based on the decision rules for DLTs, patients may be enrolled into Cohort -1. Cohort -1 will receive DEC205mAb-NY-ESO-1 fusion protein (CDX-1401) (Day 1) given with adjuvant poly-ICLC (Day 1 and Day 2) for each 28 day cycle for a total of 5 cycles, and daily oral INCB024360 100 mg BID (Cohort -1) starting on Day 1 for 7 cycles. Based on the decision rules for DLTs, patients may be enrolled into Cohort -2. Cohort -2 will receive DEC205mAb-NY-ESO-1 fusion protein (CDX-1401) (Day 1) given with adjuvant

	
poly-ICLC (Day 1 and Day 2) for each 28 day cycle for a total of 5 cycles, and daily oral INCB024360 50 mg BID (Cohort -1) starting on Day 1 for 7 cycles.
 
Phase IIb:
 
The Phase IIb component of this trial will consist of a randomized parallel design of n=25+25=50 patients =50 patients with treatment arms: (i) DEC205mAb-NY-ESO-1 fusion protein (CDX-1401) with adjuvant poly-ICLC alone and (ii) INCB024360 in combination with the DEC205mAb-NY-ESO-1 fusion protein (CDX-1401) with adjuvant poly-ICLC. Stratification will be on clinical site (Roswell Park, U. of Pittsburgh).
 
The primary endpoint will be progression free survival. Baseline is defined as the time following the treatment free interval, which can span 0 - 2 months, as described in Iasonos et al.[1] The primary analysis will be carried forth using a Cox proportional hazards model with factors corresponding to treatment and a continuous covariate adjustment for the length of the treatment free interval and a stratification factor for clinical site.
 
Exploratory Cohort Roswell Park site ONLY:
 
An additional exploratory cohort (N=6) receiving 4 cycles of sirolimus in combination with DEC205mAb-NY-ESO-01 fusion protein (CDX-1401) with adjuvant poly-ICLC will be added to supplement the secondary objectives, which will aid in planning the next phase of the investigation. This will not affect the randomized component of the study as enrollment to the randomized Phase IIb at Roswell Park only will be suspended temporarily until the 6 patients are enrolled.

Accrual Target / Duration	
Phase I: 3 – 12 patients
 
Phase IIb: 50 patients
 
Exploratory Cohort: 6 patients
 
The duration of patient enrollment is expected to be 8 years. Patients in Phase I and Phase IIb are expected to participate in the study for approximately 28 weeks of active therapy. Patients in the exploratory cohort are expected to participate in the study for approximately 20 weeks of active therapy.

Study Procedures and Observations	
Patients will have regularly scheduled study visits at the clinical site including physical exam, hematology, chemistry, and performance status-refer to Table 3 and Table 4 schedule of procedures and observations for specific time points..
 
Disease Assessment: Baseline, Cycle 4 Day 1, treatment discontinuation, and 3 and 6 months after last study drug dose.
 
Adverse Events: From first dose of study drug until 30 days (± 3 days) after the last dose of study drug.

Statistical Analysis	
• Phase I: The following decision rules will be followed: (i) If 0/3 dose limiting toxicities (DLTs) are observed proceed to enroll 3 more patients (ii) If 1/3 DLTs are observed enroll 3 more patients at the same treatment regimen. If 0/6 or 1/6 DLTs are observed, declare the regimen safe and as the maximum tolerated dose combination (MTD) of INCBO24360 in combination with the vaccine. If at least 2/3 or 2/6 DLTs are observed in Cohort 1, stop and de-escalate INCBO24360 to 100 mg BID in Cohort -1. If at least 2/3 or 2/6 DLTs are observed in Cohort -1, stop and de-escalate INCBO24360 to 50 mg BID in Cohort -2.• Phase IIb:• The Phase IIb component of this trial will consist of a randomized parallel design of n=25+25=50 patients =50 patients with treatment arms: (i) DEC205mAb-NY-ESO-1 fusion protein (CDX-1401) with adjuvant poly-ICLC alone and (ii) INCBO24360 in combination with the DEC205mAb-NY-ESO-1 fusion protein (CDX-1401) with adjuvant poly-ICLC. Stratification will be on clinical site (Roswell Park, U. of Pittsburgh). The primary endpoint will be progression free survival. Baseline is defined as the time following the treatment free interval, which can span 0 - 2 months, as described in Iasonos et al.[1] The primary analysis will be carried forth using a Cox proportional hazards model with factors corresponding to treatment and a continuous covariate adjustment for the length of the treatment free interval and a stratification factor for clinical site.• Phase I/IIb: The secondary analysis of continuous immunological response endpoints [antibody titers; NY-ESO-1 specific CD8⁺ and CD4⁺ frequency and function (IFN-γ ELISPOT and tumor recognition by CTL)] will be analyzed in a straightforward analysis-of-covariance (ANCOVA) fashion modeling post-treatment levels as a function of pre-treatment levels with factors corresponding to INCBO24360 (yes/no) and DEC205mAb-NY-ESO-1 fusion protein with adjuvant poly-ICLC (yes/no).• Exploratory Cohort: The analysis of continuous immunological response endpoints (e.g., antibody titers; NY-ESO-1 specific CD8⁺ and CD4⁺ frequency and function; frequency of memory T cell populations; TCR avidity) will be analyzed via an analysis-of-covariance (ANCOVA) fashion modeling post-treatment levels as a function of pre-treatment levels with factors corresponding to Sirolimus (yes/no) and DEC205mAb-NY-ESO-1 fusion protein with adjuvant poly-ICLC (yes/no).
----------------------	--

INVESTIGATOR STUDY ELIGIBILITY VERIFICATION FORM

Patient Name: (Network sites use subject initials) :

Medical Record No.: (Network sites use subject ID) :

Title: A Phase I/IIb Study of DEC205mAb-NY-ESO-1 Fusion Protein (CDX-1401) Given with Adjuvant Poly-ICLC in Combination with INCB024360 for Patients in Remission with Epithelial Ovarian, Fallopian Tube, or Primary Peritoneal Carcinoma Whose Tumors Express NY-ESO-1 or LAGE-1 Antigen

INCLUSION CRITERIA				
Yes	No	N/A	All answers must be "YES" or "N/A" for patient enrollment.	Date
			1. Eligible patients will be women with epithelial ovarian, fallopian tube, or primary peritoneal carcinoma after chemotherapy with no evidence of disease or minimal residual disease for primary or recurrent disease. This may or may not be measurable. These patients would normally enter a period of observation after standard management.	
			2. Any HLA type. (Historic HLA typing is permitted.)	
			3. Tumor expression of NY-ESO-1 or LAGE-1 by IHC and/or RTPCR.	
			4. Life expectancy > 6 months.	
			5. Hematology and biochemistry laboratory results within the limits normally expected for the patient population, without evidence of major organ failure. Have the following clinical laboratory values: 
• ANC \geq 1,000/μL• PLT \geq 100,000/μL• Hgb \geq 8 g/dL• Total bilirubin \leq 1.5 x ULN• Serum aspartate aminotransferase (SGOT/AST) or serum alanine aminotransferase (SGPT/ALT) \leq 3 x ULN• Serum creatinine \leq 2 x ULN	
			6. Have been informed of other treatment options.	
			7. Age \geq 18 years of age.	

INCLUSION CRITERIA				
Yes	No	N/A	All answers must be "YES" or "N/A" for patient enrollment.	Date
			8. Patient or legal representative must understand the investigational nature of this study and sign an Independent Ethics Committee/Institutional Review Board approved written informed consent form prior to receiving any study related procedure.	
			9. Have an ECOG Performance Status of \leq 2. Refer to Appendix A .	
			10. The ability to swallow and retain oral medication.	
			11. Patients of child-bearing potential must agree to use acceptable contraceptive methods (e.g., double barrier) during treatment.	
			12. Patients may have received previous NY-ESO-1 vaccine therapy. Patients who received maintenance paclitaxel or bevacizumab are eligible for enrollment provided they have discontinued therapy (at least 4 weeks for prior taxane or prior bevacizumab) prior to randomization and recovered from toxicities to less than Grade 2.	

Investigator Signature: _____

Date: _____

INVESTIGATOR STUDY ELIGIBILITY VERIFICATION FORM

Patient Name: (Network sites use subject initials) :

Medical Record No.: (Network sites use subject ID) :

Title: A Phase I/IIb Study of DEC205mAb-NY-ESO-1 Fusion Protein (CDX-1401) Given with Adjuvant Poly-ICLC in Combination with INCB024360 for Patients in Remission with Epithelial Ovarian, Fallopian Tube, or Primary Peritoneal Carcinoma Whose Tumors Express NY-ESO-1 or LAGE-1 Antigen

EXCLUSION CRITERIA				
Yes	No	N/A	All answers must be "No" or "N/A" for patient enrollment.	Date
			1. Metastatic disease to the central nervous system for which other therapeutic options, including radiotherapy, may be available.	
			2. Other serious illnesses (e.g., serious infections requiring antibiotics, bleeding disorders).	
			3. History of severe autoimmune disorders requiring use of steroids or other immunosuppressives.	
			4. Concomitant systemic treatment with chronic use (based on the investigator's judgement) of corticosteroids, anti-histamine or non-steroidal anti-inflammatory drugs, and other platelet inhibitory agents (See also Section 6.4 for restrictions/recommendations on ancillary therapy).	
			5. Chemotherapy, radiation therapy, or immunotherapy within 4 weeks prior to first dosing of study drug (6 weeks for nitrosoureas). Concomitant hormonal therapies for breast cancers are allowed.	
			6. Subjects being treated with a monoamine oxidase inhibitor (MAOI), or drug which has significant MAOI activity (e.g., meperidine, linezolid, methylene blue) within 3 weeks prior to screening.	
			7. Subjects who are currently receiving therapy with a potent CYP3A4 inducer or inhibitor (e.g. clarithromycin, telithromycin, nefazodone, itraconazole, ketoconazole, atazanavir).	
			8. Use of UGT1A9 inhibitor including: diclofenac, imipramine, and ketoconazole.	

EXCLUSION CRITERIA				
Yes	No	N/A	All answers must be "No" or "N/A" for patient enrollment.	Date
			9. Participation in any other clinical trial involving another investigational agent within 4 weeks prior to first dosing of study drug.	
			10. Known hepatitis B, hepatitis C, or HIV.	
			11. Mental impairment that may compromise the ability to give informed consent, and comply with the requirements of the study.	
			12. Lack of availability of a patient for immunological, and clinical follow-up assessment.	
			13. Evidence of current drug or alcohol abuse or psychiatric impairment, which in the Investigator's opinion will prevent completion of the protocol therapy or follow-up.	
			14. Pregnant or nursing female patients.	

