6.1.5 Compliance

CDX-1401 and poly-ICLC will be administered by the study staff on the CDX-1401 dosing dates, and may be self-administered by the patient for the remaining doses. Compliance with self-administration of adjuvants and INCB024360 (or Sirolimus for exploratory cohort) will be assessed via patient-reported dosing diaries (**Appendix C** and **Appendix D**).

Table 1. Dosing Schedule for INC024360 and DEC205mAb-NY-ESO-1 Fusion Protein (CDX-1401) Given with Adjuvant Poly-ICLC

Treatment Cohorts	Number of Patients	DEC205mAb-NY ESO 1 Fusion Protein (CDX 1401) Given with Adjuvant Poly-ICLC ^a	INC024360 (Oral)
Phase I			
Cohort -2	3 – 6 patients	
 • DEC205mAb-NY-ESO-1 fusion protein (1 mg, intracutaneous injection) on Day 1 of each 28 day cycle for a total of 5 cycles. • Adjuvant poly-ICLC (1 ml, subcutaneous) on Day 1 and Day 2 of each 28 day cycle for a total of 5 cycles. 	50 mg BID for a total of 7 cycles
Cohort -1	3 – 6 patients	
 • DEC205mAb-NY-ESO-1 fusion protein (1 mg, intracutaneous injection) on Day 1 of each 28 day cycle for a total of 5 cycles. • Adjuvant poly-ICLC (1 ml, subcutaneous) on Day 1 and Day 2 of each 28 day cycle for a total of 5 cycles. 	100 mg BID for a total of 7 cycles
Cohort 1 (start)	3 – 6 patients	
 • DEC205mAb-NY-ESO-1 fusion protein (1 mg, intracutaneous injection) on Day 1 of each 28 day cycle for a total of 5 cycles. • Adjuvant poly-ICLC (1 ml, subcutaneous) on Day 1 and Day 2 of each 28 day cycle for a total of 5 cycles. 	300 mg BID for a total of 7 cycles
Randomized Phase IIb (parallel groups design)			
Cohort 2a	25 patients	
 • DEC205mAb-NY-ESO-1 fusion protein (1 mg. intracutaneous injection) on Day 1 of each 28 day cycle for a total of 5 cycles • Adjuvant poly-ICLC (1 ml. subcutaneous) on Day 1 and Day 2 of each 28 day cycle for a total of 5 cycles.. 	None
Cohort 2b	25 patients	
 • DEC205mAb-NY-ESO-1 fusion protein (1 mg, intracutaneous injection) on Day 1 of each 28 day cycle for a total of 5 cycles. • Adjuvant poly-ICLC (1 ml, subcutaneous) on Day 1 and Day 2 of each 28 day cycle for a total of 5 cycles. 	300 mg BID for a total of 7 cycles

1 Refer to **Section 11** statistical considerations and additional decision rules.

Based on phase 1 safety review, INC024360 300 mg. po BID for a total of 7 cycles was determined the phase IIb dose level.

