6.6 Duration of Treatment

The duration of patient enrollment is expected to be 8 years.

INCB groups: Patients are expected to participate in the study for approximately 28 weeks of active therapy and follow-up assessments at 3 months, 6 months, and 12 months after the last dose of study drug. Patients may return to standard of care after completing all assessments at follow-up.

Exploratory Cohort with Sirolimus: Patients are expected to participate in the study for approximately 20 weeks of active vaccine therapy and follow-up assessments at 3 months, 6 months and 12 months after the last dose of study drug. Patients may return to standard of care after completing all assessments at End of Treatment.

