7.3 Schedule of Procedures and Observations

Clinical assessments will be performed every 4 weeks. Imaging with computed tomography (CT) or magnetic resonance imaging (MRI) will be performed according to standard of care. Performance status and AEs will be assessed at each clinical assessment until disease progression.

The schedule of procedures and observations for the INCB024360 cohorts in this study is summarized in **Table 3** below. Approximately ± 3 days are allowed for the schedule of procedures.

The schedule of procedures and observations for the exploratory cohort (with sirolimus) at Roswell Park site ONLY is summarized in Table 4.

Table 3. Schedule of Procedures and Observations (INCB024360 cohorts)

Study Event	Baseline ¹															3 Months, 6 Months, and 12 Months After Last Vaccine or dose of INCB
		Day 1	Cycle 1		Cycle 2		Cycle 3		Cycle 4		Cycle 5		Cycle 6		Cycle 7	
			Day 1	Day 2	Day 15	Day 1 ± 3 days	Day 2	Day 1 ± 3 days								
Informed Consent	X															
Medical History	X	X			X		X		X		X		X		X	
Physical Examination, vital signs and weight	X	X			X		X		X		X		X		X	
NY-ESO-1, TIL, PD-L1, and/or LAGE-1 Expression in Tumor Tissue ²	X															
HLA Typing (Historic HLA Typing is Permitted-low resolution) ³	X															
Disease Assessment ⁴	X								X							X
Hematology, PT/INR ⁶	X				X		X		X		X		X		X	
Chemistry ⁷	X				X		X		X		X		X		X	
Pharmacokinetic/Pharmacodynamic Sampling ⁸		X	X	X												
Performance Status (Appendix A)	X	X			X		X		X		X		X		X	
Tumor Markers ⁹	X	X			X		X		X		X		X		X	
Vaccination: DEC205mAb-NY-ESO-1 Fusion Protein (CDX-1401) given with Adjuvant Poly-ICLC		X			X		X		X		X					
																.1.1 Treatment discontinuation ¹³

Study Event	Baseline ¹	Cycle 1			Cycle 2			Cycle 3			Cycle 4			Cycle 5			Cycle 6			Cycle 7			.1.1 Treatment discontinuation ¹³	3 Months, 6 Months, and 12 Months After Last Vaccine or dose of INCB
		Day 1	Day 2	Day 15	Day 1 ± 3 days	Day 2	Day 1 ± 3 days	Day 2	Day 1 ± 3 days	Day 2	Day 1 ± 3 days	Day 2	Day 1 ± 3 days	Day 2	Day 1 ± 3 days	Day 2	Day 1 ± 3 days	Day 2	Day 1 ± 3 days	Day 2	Day 1 ± 3 days	Day 2		
Adjuvant Poly-ICLC (administered in clinic or at home by the patient)		X	X		X	X	X	X	X	X	X	X	X	X	X	X	X	X	X	X	X			
INC024360 ¹⁰		X	X	X	X	X	X	X	X	X	X	X	X	X	X	X	X	X	X	X				
Antibody Response: NY-ESO-1 ELISA and NY-ESO-1 Cellular Immune Response (T cell): ELISPOT and ICS ¹¹		X			X		X		X		X		X		X		X		X		X		X	

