8.3 Non-Target Lesions

All other small lesions (longest diameter < 10 mm or lymph nodes \geq 10 mm to < 15 mm short axis) and non-measurable lesions (i.e., leptomeningeal disease, ascites, pleural or pericardial effusion, inflammatory breast disease, lymphangitic involvement of skin or lung, blastic bone lesions, or abdominal masses / abdominal organomegaly identified by physical exam that is not measurable by imaging) should be identified as non-target lesions and indicated as present in the source documents at baseline. The general location will also be documented on the images drawing a regularly-shaped Region of Interest. Measurements of the non-target lesions will not be performed, but the presence or absence of each should be noted throughout follow-up and evaluation.

Those patients, who have no evidence of disease at the baseline, will be documented as no evidence of disease until progression of disease is documented per RECIST 1.1.

- **Complete Response:** Disappearance of all non-target lesions and normalization of tumor marker level, if applicable. All lymph nodes must be non-pathological in size (< 10 mm short axis).
- **Non-Complete Response/Non-Progressive Disease:** Persistence of 1 or more non-target lesion(s) and/or maintenance of tumor marker level above the upper limits of normal.
- **Progressive Disease:** Appearance of 1 or more new lesions or the unequivocal progression of existing non-target lesions. Although a clear progression of non-target lesions is exceptional, in such circumstances, the opinion of the treating physician should prevail and the progression status should be confirmed at a later time.
 - TUMOR RESPONSE ASSESSMENT BY IRRC – PHASE 2
- Tumor Response will be assessed by the Immune-related response criteria (irRC) as published by Wolchok et al. (68). Response is defined as irCR, irPR or irSD over a period of at least 4 weeks. Disease Control by irRC is defined as irSD or irPR or irCR.

PROGRESSION-FREE SURVIVAL (PFS)

Progression-free survival will be determined for each patient with time origin at the start of the treatment (day 1) until the first occurrence of confirmed progression by irRC or date of death if the patient dies from any causes before progression. Every effort will be made to follow patients for progression after they discontinue the study.

OVERALL SURVIVAL (OS)

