The Phase IIb component of this trial will consist of a randomized parallel design of $n = 25 + 25 = 50$ patients with treatment arms (i) DEC205mAb-NY-ESO-1 fusion protein (CDX-1401) with adjuvant poly-ICLC and (ii) INCB024360 in combination with the DEC205mAb-NY-ESO-1 fusion protein (CDX-1401) with adjuvant poly-ICLC. Stratification will be on clinical site (Roswell Park, U. of Pittsburgh). The primary endpoint will be progression free survival. Baseline is defined as the time following the treatment free interval, which can span 0 - 2 months, as described in Iasonos et al.[1] The primary analysis will be carried forth using a Cox proportional hazards model with factors corresponding to treatment and a continuous covariate adjustment for the length of the treatment free interval and a stratification factor for clinical site. Permuted blocked random assignment with block sizes of 4 and an allocation ratio of 1:1 for DEC205mAb-NY-ESO-1 fusion protein (CDX-1401) with adjuvant poly-ICLC alone versus INCB024360 in combination with the DEC205mAb-NY-ESO-1 fusion protein (CDX-1401) with adjuvant poly-ICLC stratified by clinical site..

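### In Phase IIb, the 3- and 6-month disease assessments are timed from the last drug dose, about 82 days later in Cohort 2b than in 2a for completers, while PFS runs from day 1; the likely effect on the hazard ratio is small and its direction open

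*Combined protocol and SAP*

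**What the plan says.** **Scan times.** The synopsis (Study Procedures and Observations) gives "Disease Assessment: Baseline, Cycle 4 Day 1, treatment discontinuation, and 3 and 6 months after last study drug dose". Section 6.6 uses the same anchor for follow-up in the INCB024360 groups: "follow-up assessments at 3 months, 6 months, and 12 months after the last dose of study drug". The last column of Table 3 (section 7.3) is headed "3 Months, 6 Months, and 12 Months After Last Vaccine or dose of INCB", and footnote 5 limits disease assessment there to months 3 and 6 in patients who have not progressed.

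**Treatment length.** In Table 1 (section 6.1.5) the vaccine schedule is the same for every cohort, with "Adjuvant poly-ICLC (1 ml, subcutaneous) on Day 1 and Day 2 of each 28 day cycle for a total of 5 cycles". Cohort 2a receives nothing else. Cohort 2b also takes INCB024360, "300 mg BID for a total of 7 cycles".

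**Endpoint and analysis.** Section 8.3 starts the PFS clock on day 1 of treatment for every patient, and adds: "Every effort will be made to follow patients for progression after they discontinue the study". Section 11.1 states: "The primary analysis will be carried forth using a Cox proportional hazards model with factors corresponding to treatment", with a covariate for the treatment-free interval and a stratification factor for site. No interval-censored analysis is mentioned.

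**Discontinuation scan.** No section dates it for Cohort 2a. Section 3.1.1 expects about 28 weeks on treatment for all Phase IIb patients, and section 6.2 defines completion as 7 cycles plus the final assessments; Table 1 gives 2a only 5 cycles. Section 8.4 ties the scan to the end of the study. Footnote 13 of Table 3 gives about 30 days after the last drug, but for concomitant medication and adverse events, not for a CT.

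**The concern.** Progression found by imaging is dated at the scan that shows it. If the arms are scanned at different times since day 1, identical disease courses yield different recorded PFS times, and a Cox model can read the difference in calendars as a difference in treatment. Both arms share the Cycle 4 Day 1 scan (Day 85). At the plan's 8-month median about 39 of the 50 patients are still progression-free then, so most of the trial enters the part of the schedule that depends on the arm.

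The unsettled discontinuation scan adds to this. Two sites could each follow the protocol and still scan Cohort 2a on different days.

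**Working it through.** **The plan's own figure.** The plan gives no figure for the effect of the scan schedule. Its only figure for the PFS design is power of 0.70 for 16 versus 8 months (section 11.1.1). It states no alpha or sidedness, so this cannot be firmly reproduced: simulation gives 0.64 to 0.65 at two-sided 0.05 and 0.76 at one-sided 0.05. The point here does not depend on it.

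**Day arithmetic, completers (28-day cycles).**
- 2a: Cycle 5 Day 1 = 4 × 28 + 1 = 113; second poly-ICLC = Day 114.
- 2b: last INCB024360 = 7 × 28 = Day 196. Gap: 196 − 114 = 82 days.
- 3 months (+91 days): 114 + 91 = 205 and 196 + 91 = 287.
- 6 months (+182 days): 114 + 182 = 296 and 196 + 182 = 378.

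**Patients affected.** Day 85 is 2.79 months. S(85) = 2^(−2.79/8) = 0.785, and 50 × 0.785 = 39.3.

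**Null simulation.** Inputs: 25 per arm (section 11.1); constant hazard and an 8-month median (section 11.1.1), applied to both arms. Section 11.1.1 attaches that median to an INCB024360-alone arm, which Phase IIb does not have; I use it as the reference value. Progression is dated at the next scan, patients without progression are censored at the last scan, and the Cox model handles ties by Efron's method. Two follow-up patterns were run:
- scheduled scans only;
- imaging continued about every 91 days after the last scheduled scan, each interval varying by up to 14 or up to 28 days (an assumption, because section 7.3 leaves imaging to standard of care).

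All rows of the table use the last-dose anchor for months 3 and 6. Values are hazard ratios, 2b versus 2a, when the true value is 1.

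| Discontinuation scan (2a / 2b) | Scheduled scans only | Later imaging, ±14 days | Later imaging, ±28 days |
|---|---|---|---|
| Last dose + 30 days (Day 144 / 226) | 0.935 | 0.988 | 0.978 |
| End of last cycle (Day 140 / 196) | 1.002 | 1.024 | 1.020 |
| At last dose (Day 114 / 196) | 1.031 | 1.042 | 1.035 |
| Week 28 in both arms (Day 196 / 196) | 1.005 | 1.028 | 1.016 |

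**Against sampling error.** With scheduled scans only, the largest shift is ln(0.935)/0.380 = −0.18 standard errors. With later imaging of variable timing it is ln(1.042)/0.291 = 0.14.

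**Rejections under the null.** With scheduled scans only, and an assumed 2.5% per side, rejections favouring INCB024360 / vaccine alone run from 3.5% / 1.6% (first row) to 1.8% / 2.9% (third row).

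**Other readings of the anchor.**
- Counting months 3 and 6 from the last vaccine in both arms, as Table 3's header permits, gives 0.97 to 1.03 with the first three discontinuation dates.
- Counting them from week 28 in both arms puts every scan on the same day (85, 196, 287, 378), so the shift is zero.

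**Common calendar.** Scans on Days 85, 169, 253 and 337 in both arms give a null hazard ratio of 1.00.

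**Not modelled.** irRC confirmation, deaths, visits triggered by progression, site strata and the treatment-free-interval covariate.

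**The case against.** The strongest reply is that the plan can be read so that little or nothing happens. Sections 3.1.1 and 6.2 give one treatment length for all of Phase IIb, Table 3 runs to Cycle 7, and Cycle 4 is the middle cycle of 7, not of 5, which fits section 8.4. On that view the discontinuation scan is at week 28 in both arms (1.005 with scheduled scans only). If follow-up also starts at week 28, the calendars coincide. This stands as a possible reading, but it strains the synopsis: the last study-drug dose in 2a is in Cycle 5. The text does not choose between the readings.

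A second reply is that imaging under standard of care, 4-weekly clinical assessments and continued follow-up for progression will blur the difference. That largely stands. If half of progressions surface at 4-weekly visits up to Day 197 (an assumption), the hazard ratio with scheduled scans only is 0.98 to 1.01. Neither provision sets an interval or aligns the arms, however.

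A reader might infer a larger effect. Imaging on an exact 91-day grid, kept separately in each arm to 5 years, gives hazard ratios up to 1.08 and apparently lower power. No passage sets such a grid. On it, each later 2b scan falls 91 − 82 = 9 days before the nearest 2a scan, every time; letting the intervals vary by 2 to 4 weeks removes about half or more of the shift. The documents do not support a claim of lost power.

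**Conclusion.** The point holds for Phase IIb completers. Under the synopsis's anchor, two of the four scheduled post-baseline disease assessments fall about 82 days later since day 1 in Cohort 2b than in 2a, and the date of 2a's discontinuation scan cannot be settled from the text. The primary endpoint's assessment schedule therefore depends on the randomised arm.

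The consequence is small: a null hazard ratio of about 0.93 to 1.03 with scheduled scans only, and about 0.98 to 1.04 with later imaging of variable timing, at most about 0.2 standard errors. These figures rest on exponential PFS with an 8-month median, progression dated at the scan, and the last-dose anchor.

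A reader might also infer that the schedule favours INCB024360. The documents do not support that: the sign changes with the discontinuation date and with imaging after treatment. Nor does the claim reach early stoppers, since footnote 4 of Table 3 leaves their CT to discretion. I would label this a cheap improvement of low to moderate priority.

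**What to change.** Reconcile the synopsis, sections 3.1.1, 6.2, 6.6 and 8.4, and Table 3 with its footnotes, on when the discontinuation assessment falls in each arm and what starts the follow-up clock. Then set Phase IIb disease assessments at the same weeks from day 1 in both arms, whatever the date drug stops, keeping four scheduled scans after baseline. The interval is the sponsor's choice; every 12 weeks (Days 85, 169, 253, 337) is one illustration that keeps the Cycle 4 Day 1 scan. Imaging after the last scheduled scan should follow one calendar in both arms. An interval-censored sensitivity analysis using actual scan dates is optional.

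The cost is a protocol amendment, with no added scheduled scans. Expected events by the last scheduled scan hardly change: 25 × (0.569 + 0.659) = 30.7 under the last-dose anchor, against 50 × 0.617 = 30.8 on the 12-week calendar.

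There are two drawbacks. Scans are no longer tied to the last-dose visit. With 12-week scans, 2a's second scan moves from Day 114–144 (the last-dose, end-of-cycle and 30-day readings) to Day 169, so its interval after Day 85 grows from 29–59 days to 84 and early progression in 2a is dated less precisely. The last scheduled scan moves from Day 296 to 337 in 2a and from Day 378 to 337 in 2b.
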